2.2 Flowchart 2: Simplified Trial Follow-up

As of Protocol Amendment 2:

Type of Visit	Local Standard of Care Visit ^a			
Informed consent/assent	Refer to the Final/Withdrawal Visit in Flowchart 1: Trial Follow-up			
Dispensation of investigational medication	X ^d			
Collection of SAEs possibly related to DRV/rtv and pregnancies ^b	X			
Study termination ^c	X			
Note: Assessments are to be performed per local standard of care and documented in the subject's medical				

records only.

The next planned visit before switching to simplified data collection as per Protocol Amendment 2 will be a

The next planned visit after approval of Protocol Amendment 2 will be a Final/Withdrawal Visit. During this Final/Withdrawal Visit, the informed consent will be signed, final assessments will be carried out and recorded in the CRF, and the study medication will be dispensed as described in Flowchart 1: Trial Follow-up. All subsequent visits and assessments will be performed per local standard of care and documented in the subject's medical records only. Investigators will continue to report SAEs possibly related to DRV/rtv and pregnancies to the sponsor using regular pharmacovigilance reporting. This information will only be entered in the company safety repository.

If the subject exits the trial, the last visit will be a local standard of care visit but without dispensation of investigational medication.

^a The next planned visit before switching to simplified data collection as per Protocol Amendment 2 will be a Final/Withdrawal Visit. During this Final/Withdrawal Visit, the informed consent will be signed, final assessments will be carried out and recorded in the CRF, and the study medication will be dispensed as described in Flowchart 1: Trial Follow-up.

^b Investigators will continue to report SAEs possibly related to DRV/rtv and pregnancies to the sponsor using regular pharmacovigilance reporting.

^c Study termination will be documented in the subject's medical records and recorded on a separate, paper termination disposition form to be shared with the sponsor.

^d If the subject exits the trial, the last visit will be a local standard of care visit but without dispensation of investigational medication.

3 INTRODUCTION

Inhibitors of human immunodeficiency virus (HIV) protease have become cornerstones in the treatment of HIV disease, particularly in HIV-1 infected subjects with a long history of antiretroviral (ARV) therapy. Current options for the treatment of HIV-1 infected adult subjects consist of nucleoside/nucleotide reverse transcriptase inhibitor (NRTIs), non-nucleoside reverse transcriptase inhibitor (NNRTIs), protease inhibitors (PIs), entry inhibitors, and an integrase inhibitor. A triple regimen is considered standard of care and when effective, results in suppression of the virus below the detection limits of the current tests, thereby strongly reducing the emergence of resistance.

Darunavir (DRV, formerly known as TMC114) is an HIV PI with potent in vitro activity against wild-type HIV-1, and, as a result of the drug-screening program aimed at activity against resistant strains of HIV-1, also active against a large panel of viruses resistant to currently licensed PIs.

DRV, co-administered with low dose ritonavir is indicated in combination with other antiretroviral medicinal products for the treatment of human immunodeficiency virus (HIV-1) infection in adult and pediatric patients from the age of 3 years. DRV was first registered in the United States (June 2006) and has obtained marketing authorization in Europe in February 2007. The approved indications and registered tablet strengths for DRV vary per country where registered.

DRV has been approved based on the below mentioned clinical trials in the following populations:

ADULT HIV-Infected subjects:

In ARV-experienced: Studies TMC114-C202, TMC114-C213, TMC114-C215, TMC114-C214 In ARV-experienced without DRV resistance-associated mutations (RAMs): Trial TMC114-TiDP31-C229

In ARV-naive subjects: Trial TMC114-C211

The adult patients could roll-over to trial TMC114IFD3001 for access to DRV if not yet accessible by other means in their country.

PEDIATRIC HIV-Infected subjects:

In ARV-experienced adolescents: Trial TMC114-C212

In ARV-naive adolescents: Trial TMC114-C230

In ARV-experienced subjects aged 3 years to 6 years: Trial TMC114-C228

The pediatric patients could roll-over to trial TMC114-TiDP29-C232 for access to DRV if not yet accessible by other means in their country.

For detailed and updated information on the clinical trial data, refer to the most recent Investigator's Brochure (IB) of DRV.²

The aim of the present amended trial TMC114IFD3001 is to provide continued access to DRV/rtv for adult and pediatric subjects who previously received DRV/rtv in the above-mentioned clinical (parent) trials, who continue to benefit from treatment with DRV and cannot have access to DRV in their country by other means.

4 TRIAL OBJECTIVES

4.1 Primary Objective

The primary objective of this trial is to continue the provision of DRV/rtv for adult and pediatric subjects who previously received DRV/rtv in the clinical (parent) trials TMC114-C211, TMC114-C214, TMC114-TiDP31-C229 or in the pediatric (parent) trial TMC114-TiDP29-C232, who continue to benefit from the use of DRV/rtv, in countries where DRV is not commercially available for the subject, is not reimbursed, or cannot be accessed through another source (e.g., access program, governmental program).

In addition, the long-term safety and tolerability of DRV/rtv in combination with other ARVs will be assessed.

Protocol Amendment 2 Objective:

As of Protocol Amendment 2, the objective of the trial is to provide DRV through this trial until the subjects can be switched to locally available DRV-based treatment regimens (ie, commercially available and reimbursed, or accessible through another source [eg, access program or government program]) or to local standard of care, as appropriate.

5 METHODS

5.1 Trial Design

5.1.1 OVERVIEW OF TRIAL

This is a continued access trial for adult and pediatric subjects who have completed treatment with DRV/rtv in the adult clinical (parent) trials TMC114-C211, TMC114-C214, TMC114-TiDP31-C229 or in the pediatric (parent) trial TMC114-TiDP29-C232, who continue to benefit from the use of DRV/rtv, and who live in a country where DRV is not accessible.

At the baseline visit, inclusion and exclusion criteria will be checked to confirm eligibility. Once the eligibility criteria are met, subjects will continue treatment as follows:

- HIV-1 infected subjects participating in the TMC114-C211(parent) trial or in the pediatric (parent) trial TMC114-TiDP29-C232, after original participation in TMC114-TiDP29-C230 trial will continue on the DRV/rtv 800/100 mg q.d. dosing regimen as administered in the original (parent) trial.
- HIV-1 infected subjects participating in the pediatric (parent) trial TMC114-TiDP29-C232, after original participation in TMC114-C212 or TMC114-TiDP29-C228 trial will continue on the selected b.i.d. DRV/rtv dosing regimen as administered in the original (parent) trial, or on an adjusted dose if necessary due to a change in body weight.

HIV-1 infected subjects participating in the TMC114-C214 or TMC114-TiDP31-C229 (parent) trials will continue on the DRV/rtv 600/100 mg b.i.d. dosing regimen as administered in the original (parent) trial.

Visits and assessments are performed, according to local generally accepted standard of care, but desirable every 3 months for pediatric subjects and not less frequent than every 6 months for adult subjects. The interval between 2 consecutive visits should not exceed 6 months for pediatric subjects. Adverse events (AEs) considered at least possibly related to DRV/rtv, AEs leading to discontinuation or treatment interruption, serious AEs (SAEs), and pregnancies (or all AEs if applicable per local regulation) will be recorded at each visit. Subjects will be instructed to report any AEs to the investigator, who reports SAEs within 24 hours to the sponsor (see Part II, Section 1.4 'Reporting of Adverse Events and HIV-Related Events').

Details on the timing of treatment and assessments are provided in the flowchart in Section 2. In addition to the assessments in this flowchart, the following assessments are recommended to be performed locally every 3 months or according to local generally accepted standard of care:

- Efficacy assessments (immunology and plasma viral load); and
- Laboratory safety assessments (hematology and biochemistry, including pancreatic amylase [if available] or lipase and lipid analyses).

As per Protocol Amendment 2, the next planned visit will be a Final/Withdrawal Visit, which will be the last visit with data collection. Thereafter, visits and assessments will be performed per local standard of care and documented in the subject's medical records only. Investigators will continue to report SAEs possibly related to DRV/rtv and pregnancies to the sponsor using regular pharmacovigilance reporting. This information will only be entered in the company safety repository.

If the subject exits the trial, the last visit will be a local standard of care visit but without dispensation of investigational medication.

Treatment will be continued until one of the following criteria is met (whichever occurs first):

- Virologic failure;
- Treatment-limiting toxicity;
- Loss to follow-up;
- Withdrawal of consent/assent by the subject or withdrawal of consent by the parent(s)/legal representative(s);
- Pregnancy;
- Termination of the trial by the sponsor;
- A DRV-based treatment regimen becomes commercially available for the subject and is reimbursed, or can be accessed through another source (e.g., access program, government program) in the region the subject is living in or subjects can be switched to local standard of care, as appropriate.

A post-treatment follow-up contact is to be performed 4 weeks after the last dose of trial medication for subjects with an ongoing adverse event, that discontinue the trial under Protocol Amendment 1, as specified in the flowchart in Section 2.

5.1.2 DISCUSSION OF TRIAL DESIGN

The primary objective of this trial is to continue the provision of DRV/rtv to subjects who have completed treatment with DRV/rtv in the adult clinical (parent) trials TMC114-C211, TMC114-C214, TMC114-TiDP31-C229 or in the pediatric (parent) trial TMC114-TiDP29-C232, who continue to benefit from the use of DRV/rtv, and who live in a country where DRV is not commercially available, is not reimbursed, or cannot be accessed through another source (e.g., access program, government program).

Selected safety data are to be collected during DRV/rtv treatment (see Section 5.4.4). Additional assessments not included in this protocol can be done locally as per local standard of care.

As per Protocol Amendment 2, the next planned visit will be a Final/Withdrawal Visit, which will be the last visit with data collection. Thereafter, visits and assessments will be performed per local standard of care and documented in the subject's medical records only. SAEs possibly related to DRV/rtv and information on pregnancies will continue to be reported to the sponsor using regular pharmacovigilance reporting. This information will only be entered in the company safety repository.

If the subject exits the trial, the last visit will be a local standard of care visit but without dispensation of investigational medication.

5.1.3 SELECTION OF DOSE(S) IN THE TRIAL

Subjects will continue on the DRV/rtv dosing regimen as administered in the original (parent) trial i.e., DRV/rtv 800/100 mg q.d. for HIV-infected subjects from the TMC114-C211 (parent) trial or from the pediatric (parent) trial TMC114-TiDP29-C232; the selected b.i.d. DRV/rtv dosing regimen for HIV-infected subjects from the pediatric (parent) trial TMC114-TiDP29-C232 with weight-based dose adjustment if necessary (see Section 5.3.3); and DRV/rtv 600/100 mg b.i.d. for HIV-infected subjects from the TMC114-C214 or TMC114-TiDP31-C229 (parent) trial.

5.2 Trial Population

5.2.1 SAMPLE SIZE

Not applicable.

Subjects who previously received treatment with DRV/rtv in the clinical (parent) trials TMC114-C211, TMC114-C214, TMC114-TiDP31-C229 or in the pediatric (parent) trial TMC114-TiDP29-C232, who continue to benefit from the use of DRV/rtv, and who live in a country where DRV is not accessible may be eligible to continue treatment with DRV/rtv via this trial.

5.2.2 INCLUSION CRITERIA

Subjects who meet all of the following criteria are eligible for this trial:

- 1. "Criterion modified per Amendment 1"
- 1.1 Male or female subjects, aged 3 years and above.
- 2. "Criterion modified per Amendment 1"

- 2.1 Subjects treated with DRV/rtv who have successfully completed the TMC114-C211, TMC114-C214, TMC114-TiDP31-C229 (parent) trial or the pediatric (parent) trial TMC114-TiDP29-C232 and in the opinion of the investigator continue to receive benefit from using DRV/rtv.
- 3. DRV is not commercially available for the subjects, is not reimbursed, or cannot be accessed through another source (e.g. access program, government program) in the region the subject is living in.
- 4. "Criterion modified per Amendment 1"
- 4.1 Subject (where appropriate, depending on age) and the parent(s) or legal representative(s) have signed the Informed Consent/Assent Form voluntarily. Children will be informed about the program and asked to give assent (where appropriate, depending on age).

5.2.3 EXCLUSION CRITERIA

Subjects meeting 1 or more of the following criteria cannot be selected:

- 1. Any condition (including but not limited to alcohol and drug use) which, in the opinion of the investigator, could compromise the subject's safety or adherence to treatment with DRV/rtv.
- 2. Any active clinically significant disease (e.g., pancreatitis, cardiac dysfunction) or findings of medical history, laboratory or physical examination that, in the investigator's opinion, would compromise the subject's safety during treatment with DRV/rtv.
- 3. Previously demonstrated clinically significant allergy or hypersensitivity to any of the excipients of the investigational medication (DRV) or ritonavir.
- 4. Pregnant or breastfeeding female subjects.
- 5. Female subject of childbearing potential without use of effective non-hormonal birth control methods or not willing to continue practicing these birth control methods for at least 30 days after the end of the treatment period.

Note: Estrogen hormonal based contraception may not be reliable when taking DRV/rtv, therefore to be eligible for this trial female subjects of childbearing potential should either:

- a. Use a double-barrier method to prevent pregnancy (i.e., use a male condom with either diaphragm or cervical cap)*; or
- b. Use non-estrogen hormonal based contraceptives in combination with a barrier contraceptive (i.e., male condom, diaphragm or cervical cap, or female condom); or
- c. Use an intra-uterine device (IUD) in combination with a barrier contraceptive (i.e., male condom, diaphragm or cervical cap, or female condom); or
- d. Be non-heterosexually active, practice heterosexual abstinence, or have a vasectomized partner (confirmed sterile).
 - *A male and female condom should not be used together due to the risk of breakage or damage caused by latex friction.

Women who are postmenopausal for at least 2 years, women with total hysterectomy, and women with tubal ligation are considered of non-childbearing potential.

6. Heterosexually active male subject not using effective birth control methods or not willing to continue practicing these birth control methods during the trial and until 30 days after the end of the trial (or after last intake of investigational medication).

5.2.4 PROHIBITIONS AND RESTRICTIONS

It is the investigator's responsibility to provide appropriate counseling to HIV-1 infected subjects about taking the necessary precautions to reduce the risk of transmitting HIV.

Since the effects of DRV/rtv on gestation are unknown, heterosexually, non-vasectomized male subjects, who are sexually active and/or female subjects of child-bearing potential having heterosexual intercourse should receive counseling about birth control methods⁷ and be advised to use one of the following birth control methods as outlined above in the exclusion criteria (Section 5.2.3). Girls having their first menses during the trial should receive counseling as well.

Female subjects should not breastfeed when taking DRV/rtv, since the effects to the newborn child are unknown. Female subjects who have a newborn child should talk to their physician about the best way to feed their child. They should be aware that HIV could be transmitted through breastfeeding.

The above precautions and restrictions apply from baseline onwards, until at least 30 days after the last intake of investigational medication.

Investigators should follow the guidance in the most recent Investigator's Brochure² regarding any contraindications, precautions for use, and other restrictions.

For detailed and updated information on the clinical trial data with regard to the reproductive toxicity of DRV, refer to the most recent Investigator's Brochure (IB) of DRV².

5.2.5 REMOVAL OF SUBJECTS FROM THERAPY OR ASSESSMENT

A subject **may** be withdrawn from the trial if:

- 1. An SAE occurs.
- 2. The subject fails to comply with the protocol requirements or to cooperate with the investigator.
- 3. The subject starts disallowed treatment (see Section 5.3.12). The sponsor should be contacted to evaluate the need for withdrawal.
- 4. The subject demonstrates lack or loss of treatment response during the trial.

A subject **must** be withdrawn from the trial if:

- 1. The parent(s) or legal representative(s) withdraw(s) consent, or the subject withdraws consent or assent.
- 2. The investigator considers it, for safety reasons, in the best interest of the subject that he or she be withdrawn.
- 3. Pregnancy has been determined.
- 4. The subject is diagnosed with acute hepatitis A, B, or C infection after baseline. For details on monitoring and management of hepatitis, see Section 5.5.4.

- 5. The subject experiences a grade 3 or 4 cutaneous reaction/rash (according to the DAIDS scale; see Section 7.2, Addendum 2: DAIDS Grading Table). For details on monitoring and management of cutaneous reaction/rash, see Section 5.5.1.
- 6. The subject experiences a grade 4 AE considered at least possibly related to DRV/rtv or a confirmed grade 4 laboratory abnormality (according to the Division of AIDS [DAIDS] scale; see Section 7.2, Addendum 2: DAIDS Grading Table) considered at least possibly related to DRV/rtv. Exceptions are, unless clinical assessment foresees an immediate health risk to the subject:
- 7. Subjects with asymptomatic triglyceride grade 4 elevations (see Section 5.6.2). The subject experiences a persistent grade 3 or 4 glucose elevation despite appropriate anti-hyperglycemic treatment (except if the subject has pre-existing diabetes; see Section 5.6.1)
- 8. The subject experiences a confirmed grade 4 pancreatic amylase elevation or a confirmed grade 3 or grade 4 lipase elevation, which persists after 14 days after the interruption of the trial medication, or if the toxicity recurs more than twice (see also Section 5.6.5.2). The subject experiences, after trial medication interruption because of a confirmed grade 3 increase in alanine aminotransferase (ALT) or aspartate aminotransferase (AST), a confirmed recurrence of grade 3 or 4 increase in ALT or AST. For subjects with hepatitis B or C coinfection present at baseline, refer to Section 5.5.3 for toxicity management plans.
- 9. The subject experiences a grade 3 or 4 acute systemic allergic reaction (according to the DAIDS scale; see Section 7.2, Addendum 2: DAIDS Grading Table). For details on monitoring and management of acute systemic allergic reactions, refer to Section 5.5.2.
- 10. A DRV-based treatment regimen becomes commercially available for the subject and is reimbursed, or can be accessed through another source (e.g., access program, government program) in the region the subject is living in or subjects can be switched to local standard of care, as appropriate.

The date and reason for discontinuation must be noted on the Case Report Form (CRF). Unless the parent(s)/legal representative(s) or subject withdraw(s) consent/assent, each subject prematurely discontinuing the trial must be seen for a final evaluation (withdrawal visit). A post-treatment follow-up contact is to be performed 4 weeks after the last dose of trial medication for subjects with an ongoing adverse event, that discontinue the trial under Protocol Amendment 1, as specified in the flowchart in Section 2. After the last visit, the Trial Termination page and Investigator's Signature page of the CRF is to be completed.

As per Protocol Amendment 2, study termination will be documented in the subject's medical records and recorded on a separate, paper termination disposition form to be shared with the sponsor.

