5.5.8 OTHER TOXICITIES

Grade 1

Subjects who develop a grade 1 AE or toxicity may continue intake of the trial medication.

Grade 2

Subjects who develop a grade 2 AE or toxicity may continue intake of the trial medication based on the investigator's clinical judgment.

Note: For grade 3 or 4 laboratory toxicities, subjects should have a confirmatory measurement within 48 hours after the laboratory results become available. This management scheme is for confirmed laboratory abnormalities and not for isolated events.

Grade 3

Subjects who develop a grade 3 AE or toxicity should interrupt all medications (including DRV/rtv and OBR) and may resume all therapy when the AE or laboratory abnormality resolved to within one grade level (\leq grade 2) of the subject's baseline. The following exceptions apply:

- subjects who experience an asymptomatic glucose elevation of grade 3 (See Section 5.6.1);
- subjects who experience asymptomatic triglyceride or cholesterol elevations of grade 3 (See Section 5.6.2);
- subjects who experience asymptomatic pancreatic amylase elevations of grade 3 with no past or active history of pancreatitis (provided lipase is within normal limits) (See Section 5.6.5);
- subjects who experience an AE that is considered not related or doubtfully related to the study medication.

Grade 4

Subjects experiencing a grade 4 AE or toxicity will permanently discontinue medication (including DRV/rtv and OBR).

The following exceptions apply:

- subjects who experience asymptomatic triglycerides elevations of grade 4 (see also Section 5.2.5);
- subjects who experience an AE that is considered not related or doubtfully related to the trial medication.

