5.6.5.2 Laboratory Abnormalities

For asymptomatic grade 1 and grade 2 pancreatic amylase and/or lipase elevations, and confirmed asymptomatic grade 3 pancreatic amylase elevations with no past or active history of pancreatitis, subjects should be carefully evaluated and followed closely.

For confirmed grade 4 elevations of pancreatic amylase and/or confirmed grade 3 or 4 elevations of lipase, subjects should interrupt therapy (including DRV/rtv and background regimen) until amylase returns to grade ≤ 2 , at which time therapy could be reintroduced. The NRTI(s) most likely related to the elevated lipase will be switched to another NRTI (see Section 5.3.5). If grade 4 elevations of pancreatic amylase and/or grade 3 or 4 lipase levels persist ≥ 14 days following interruption of therapy, or if the toxicity recurs more than twice, therapy (including DRV/rtv and background regimen) should be discontinued.

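### A related, confirmed grade 4 amylase or lipase elevation that settles on interruption means withdrawal under 5.2.5 criterion 6 and 5.5.8, but a possible restart under 5.6.5.2

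*Protocol*

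**What the plan says.** All references are to Part I of the Protocol unless the SAP is named.

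- **5.2.5, criterion 6** (a subject must be withdrawn). Besides grade 4 adverse events, it covers "or a confirmed grade 4 laboratory abnormality (according to the Division of AIDS [DAIDS] scale"), when judged at least possibly related to DRV/rtv. It closes with "Exceptions are, unless clinical assessment foresees an immediate health risk to the subject" and a colon. The one exception that follows is printed at the start of item 7: "Subjects with asymptomatic triglyceride grade 4 elevations (see Section 5.6.2").
- **5.2.5, criterion 8** (same list). The trigger reads "The subject experiences a confirmed grade 4 pancreatic amylase elevation or a confirmed grade 3 or grade 4 lipase elevation, which persists after 14 days", counted from the day on which trial drug is stopped. More than two recurrences is the alternative trigger, and the criterion points to 5.6.5.2. It does not mention relatedness.
- **5.5.8, grade 4.** "Subjects experiencing a grade 4 AE or toxicity will permanently discontinue medication (including DRV/rtv and OBR"). The exceptions are asymptomatic grade 4 triglycerides and adverse events not related or doubtfully related. The grade 3 list in the same section has an amylase exception that points to 5.6.5; the grade 4 list has none for amylase or lipase.
- **5.6.5.2.** For confirmed grade 4 amylase, or confirmed grade 3 or 4 lipase, therapy is interrupted until amylase is back to grade 2 or lower, "at which time therapy could be reintroduced". Therapy is discontinued if the elevation lasts 14 days or more after interruption, or if it recurs more than twice.
- **7.2, Addendum 2.** Grade 4 is above 5.0 x ULN for both pancreatic amylase and lipase.

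**The concern.** Criterion 6 and 5.5.8 act on the first confirmed, related grade 4 result and set no waiting period. Section 5.6.5.2 takes the same result, interrupts, and lets treatment start again. No section says which prevails, so two sites could each point to protocol text and handle identical subjects differently.

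Two things are at stake. First, the trial exists to supply DRV/rtv to people who cannot otherwise obtain it (4.1), so withdrawal ends that supply. Second, adverse events leading to discontinuation and the reasons for discontinuation are named safety summaries (5.7.2.3; SAP 3.2 and 4.1.1). Whether an event counts there would depend partly on which section the site followed.

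**Working it through.** No sample size, power or event figure is involved. The check is to trace defined cases through the four rules, including every listed exception.

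| Case (confirmed elevation) | 5.2.5 criterion 6 | 5.5.8 grade 4 | 5.6.5.2 | 5.2.5 criterion 8 | Same outcome? |
|---|---|---|---|---|---|
| A. Grade 4, related, settles within about 14 days of interruption, recurs at most twice | Withdraw | Discontinue permanently | Interrupt; restart permitted | Not met | **No** |
| B. Grade 4, related, persists about 14 days or recurs more than twice | Withdraw | Discontinue permanently | Discontinue | Withdraw | Yes in the end; timing differs |
| C. Grade 4, not or doubtfully related | Does not apply | Excepted | Applies | Applies if condition met | No conflict |
| D. Grade 3 lipase | Does not apply | Does not apply | Applies | Applies if condition met | No conflict |

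I write about 14 days because criterion 8 speaks of persistence after 14 days and 5.6.5.2 of 14 days or more.

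**Size of the gap in case A.** Under criterion 6 the number of restarts is 0. Under 5.6.5.2 the recurrence limit is passed at the third recurrence, so at most 2 recurrences are tolerated. That is up to 1 + 2 = 3 grade 4 episodes without reaching the limit, provided none persists.

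**Could the misnumbering hide an amylase or lipase exception to criterion 6?** Items 6 to 8 are visibly displaced. The triglyceride exception is fused with the glucose criterion in item 7, and the amylase/lipase criterion with the ALT/AST criterion in item 8. But the amylase/lipase sentence is built as a withdrawal trigger, not as an exception. Section 5.5.8, which is not damaged in this way, also omits amylase and lipase from its grade 4 exceptions and refers back to 5.2.5 only for triglycerides.

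**Could 5.6.5.2 be meant only for toxicity of the background regimen?** It does call for a change of the suspected NRTI. However, the introduction to 5.6 says that a DRV contribution to the events it covers cannot be ruled out, and 5.6.5.2 does not divide cases by cause. Section 5.6.3 on lactic acidosis does divide them, which shows how the protocol writes such a split when one is intended.

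**Effect on the outputs.** In case A, a withdrawn subject enters the table of adverse events leading to discontinuation (SAP 4.1.1) and the reasons for discontinuation (SAP 3.2). A restarted subject enters neither on account of this event.

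**The case against.** Several points on the other side have weight.

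- **Criterion 8.** A reader might infer that criteria 6 and 8 contradict each other. They do not. Each is a separate sufficient trigger for withdrawal, and criterion 8 exempts nobody from criterion 6. It also keeps a purpose of its own in cases C and D. It only presupposes the interruption and restart that 5.6.5.2 sets out. This stands, and the conflict lies between criterion 6 with 5.5.8 on one side and 5.6.5.2 on the other.
- **Permissive wording and discretion.** Section 5.6.5.2 allows a restart without ordering one, and the introductions to 5.5 and 5.6 leave toxicity management to the investigator. A site could satisfy every section by interrupting and never restarting. But the discretion attaches to 5.5 and 5.6; the mandatory list in 5.2.5 is not softened. A site that used the permission in 5.6.5.2 would breach criterion 6.
- **Specific over general.** Section 5.5.8 is a residual section, and amylase and lipase have their own. That reading is natural, but the protocol does not state it. Section 5.5.8 names its exceptions one by one, including several toxicities handled in 5.6, and stops at grade 3 for amylase. Criterion 6 is not a residual rule at all.
- **Analytic weight.** A reader might infer that subjects move from a discontinuation table to an interruption table. The SAP plans no table of adverse events leading to interruption, so the effect is presence in or absence from the discontinuation summaries. A related grade 4 adverse event in the treatment phase would still appear in the tables for related events and for events of at least grade 3. Laboratory testing is local and only desirable (5.4.4.2), and local safety laboratory results are not in the database (SAP 1.2).
- **Forward effect.** Under Amendment 2 the next planned visit is the last with CRF data, and toxicity management then follows local standard of care. This limits the effect on future data. Earlier follow-up was exposed, and nothing suspends the 5.2.5 criteria for subjects who remain on trial drug.

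**Conclusion.** The inconsistency is real and narrow. It concerns confirmed grade 4 amylase or lipase elevations, at least possibly related to DRV/rtv, that settle within about 14 days of interruption and recur no more than twice. For these, criterion 6 and 5.5.8 end treatment and 5.6.5.2 permits a restart.

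A reader might infer that every related grade 4 elevation is affected. The documents do not support that: events that persist or recur more than twice end in discontinuation by either route. Grade 3 lipase and events not or doubtfully related also fall outside the conflict.

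The documents give no event count, so the number of subjects concerned is unknown and may be small. The conclusion assumes that the triglyceride exception printed under item 7 belongs to criterion 6, as 5.5.8 indicates, and that no unstated order of precedence applies. It takes no view on which clinical rule is right.

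**What to change.** Reconcile 5.2.5 criterion 6 and 5.5.8 grade 4 with 5.6.5.2, and bring the related wording of criterion 8 into line, so that one rule applies to this case wherever it is read. Repair the numbering of 5.2.5 items 6 to 8 so that the exceptions to criterion 6, and each separate withdrawal criterion, can be identified. The sponsor's clinical team decides which rule governs.

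The cost is about one line in 5.2.5 and one in 5.5.8, plus the renumbering. The planned SAP tables need not change.
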